7.3. Secondary Efficacy Analyses

7.3.1. Endpoint / Variables

[Endpoint / Parameter/ Display Type]	Absolute					
	Stats Analysis		Summary		Individual	
	T	F	T	F	F	L
Hgb						
Hgb (g/dL) at each assessment visit			Y	Y		Y
Hgb (g/dL) at each assessment visit by Prior ESA ^[1] and baseline Hgb			Y	Y ^[9]		
Change from baseline in Hgb (g/dL) at each assessment visit			Y	Y		
Change from baseline in Hgb (g/dL) at each assessment visit by Prior ESA ^[1] and baseline Hgb			Y	Y ^[9]		
Number (%) of subjects by Hgb change from baseline category at Week 2 and 4 ^[2]			Y			
Number (%) of subjects by Hgb change from baseline category at Week 2 and 4 by Prior ESA ^{[1][2]} and baseline Hgb			Y			
Number (%) of subjects with Hgb level within the target range at each assessment visit ^[3]			Y	Y		
Time (%) in Hgb target range during the primary efficacy evaluation period ^{[4][6]}			Y			Y
Time (%) in Hgb target range during the primary efficacy evaluation period by prior ESA use ^{[4][6]}			Y			
Time (days) to reach the lower Hgb target (11.0 g/dL) ^{[5][6]}			Y	Y		Y
Time (days) to reach the lower Hgb target (11.0 g/dL) by prior ESA use ^{[5][6]}			Y	Y		
Number (%) of subjects who have an Hgb level of less than 7.5 g/dL ^[6]			Y			Y
Number (%) of subjects who have an Hgb level of less than 7.5 g/dL by prior ESA use ^[6]			Y			
Number (%) of subjects who have an Hgb increase of more than 2.0 g/dL over any 4 weeks			Y			Y
Number (%) of subjects who have an Hgb increase of more than 2.0 g/dL over any 4 weeks by prior ESA use			Y			
Number (%) of subjects who have an Hgb level of more than 13.0 g/dL and number of episodes ^[6]			Y			Y
Number (%) of subjects who have an Hgb level of more than 13.0 g/dL and number of episodes by prior ESA use ^[6]			Y			

[Endpoint / Parameter/ Display Type]	Absolute					
	Stats Analysis		Summary		Individual	
	T	F	T	F	F	L
Hemocue Hgb						Y
Scatter Plot of Hgb Assessments: Central Laboratory vs. HemoCue				Y		
Dose adjustment						
Dose (mg or µg) at each assessment visit / final visit			Y			Y
Dose (mg or µg) at each assessment visit / final visit by prior ESA ^[1]			Y			
Duration (days) of treatment interruption due to Hgb >13.0 g/dL			Y			Y
Duration (days) of treatment interruption due to Hgb >13.0 g/dL by prior ESA use			Y			
Dose adjustment			Y			
Dose adjustment by prior ESA use			Y			
Number of dose adjustment to reach the lower Hgb target (11.0 g/dL)			Y			
Number of dose adjustment to reach the lower Hgb target (11.0 g/dL) by prior ESA use			Y			
Number (%) of subjects with each dose at each assessment visit			Y	Y		
Number(%) of subjects with each dose at each assessment visit by prior ESA ^[1]			Y	Y		
Hgb and Dose						
Profiles of Hgb and dose over time					Y	
Iron Use						
Dose of oral iron (mg) during the treatment period and the primary efficacy evaluation period (Week 40 to 52)			Y			
Change from baseline in dose of oral iron (mg) during the treatment period and the primary efficacy evaluation period			Y			
Dose of oral iron (mg) during the treatment period and the primary efficacy evaluation period (Week 40 to 52) by Baseline Iron Use			Y			
Number (%) of subjects who use iron during the treatment period and the primary efficacy evaluation period (Week 40 to 52)			Y			
Number (%) of subjects who use iron during the treatment period and the primary efficacy evaluation period (Week 40 to 52) by Baseline Iron Use			Y			

[Endpoint / Parameter/ Display Type]	Absolute					
	Stats Analysis		Summary		Individual	
	T	F	T	F	F	L
Iron Parameters (ferritin, TSAT, hepcidin, serum iron, TIBC)						
Raw observed value at each assessment visit			Y	Y		Y
Raw observed value at each assessment visit by Subgroup ^[7]			Y	Y		
Change from baseline at each assessment visit	Y	Y	Y			
Change from baseline at each assessment visit by Subgroup ^[7]	Y	Y ^[8]	Y			

NOTES :

- T = Table, F = Figure, L = Listing, Y = Yes display generated.
- Stats Analysis = Represents TFL related to any formal statistical analyses (i.e. modelling) conducted.
- Summary = Represents TFL related to any summaries (i.e. descriptive statistics) of the observed raw data.
- Individual = Represents FL related to any displays of individual subject observed raw data.

[1] prior ESA use, prior ESA dose, prior ESA type, and ERI

[2] <=-1, >-1 to -0.5, >-0.5 to 0, >0 to 0.5, >0.5 to 1, >1 g/dL, within ± 0.5 g/dL and over ± 1 g/dL for Week 2

<=-2, >-2 to -1, >-1 to 0, >0 to 1, >1 to 2, >2 g/dL, within ± 1 g/dL and over ± 2 g/dL for Week 4

[3] Not only within the target range, but also with above and below target range will be assessed.

[4] Rosendaal method will be used (See Section 15.6.3).

[5] Kaplan-Meier method will be used to estimate P25, median and P75. Subjects within target range at baseline and subjects who could not reach lower target will be regarded as censored.

[6] On-therapy Hgb values observed at scheduled visits will be included in a summary. On-therapy Hgb values observed at unscheduled visits will be included if specified (See Section 7.3.2).

[7] Only baseline iron use, prior ESA use

[8] Only baseline iron use

[9] Only prior ESA use and baseline Hgb

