The time (weeks and percent) within/above/below the target range will be summarized by treatment group using mean, standard deviation, minimum, P25, median, P75, and maximum. For the ITT population, the treatment differences (daprodustat – epoetin beta pegol) and the associated 95% CIs for the time (weeks and percentage) within the target range will also be provided. See Section 15.6.3 for details. The summary will also be provided by prior ESA use.

Time (in days) to reach the lower Hgb target (11.0 g/dL)

The time (days) to reach the lower Hgb target will be summarized by treatment group using P25, median, and P75 by Kaplan-Meier method. Kaplan-Meier plot of time to event will be provided using on-therapy Hgb values including unscheduled visits. Subjects who could not reach lower target will be regarded as censored. Subjects who have baseline central laboratory Hgb ≥ 11.0 g/dL will be excluded in this analysis. The summary will also be provided by prior ESA use.

Number (%) of subjects who have an Hgb level of less than 7.5 g/dL

The number and percentage of subjects who have an Hgb level of less than 7.5 g/dL during the treatment period will be summarized by treatment group. On-therapy Hgb values observed in both scheduled and unscheduled visits will be included in the summary.

Number (%) of subjects who have an Hgb increase of more than 2.0 g/dL over any 4 weeks

The number and percentage of subjects who have an Hgb increase of more than 2.0 g/dL over any 4 weeks (excluding Week 2) during the treatment period will be summarized by treatment group. For the ITT population, the odds ratio (daprodustat/epoetin beta pegol) will also be provided with its 95% CI. On-therapy Hgb values will be used for the summary. See Section 15.6.3 for details.

Number (%) of subjects who have an Hgb level of more than 13.0 g/dL and number of episodes

The number and percentage of subjects who have an Hgb level of more than 13.0 g/dL during the treatment period and number of episodes will be summarized by treatment group. On-therapy Hgb values observed in both scheduled and unscheduled visits will be included in the summary.

Scatter plot of Hgb assessments: Central Laboratory vs. HemoCue

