7.3.4. Strategy for Intercurrent (Post-Randomization) Events

Any intercurrent events are taken to be irrelevant for secondary endpoints and the secondary endpoints will be summarized based on available and observed data.

Analysis of change from baseline in the respective iron parameter at each assessment visit will follow the strategy below.

Intercurrent events	Strategy
Study withdrawal / Intermittent missing	The following hypothetical scenario is considered to assess what would have happened if the event did not occur. Analysis using MMRM assume missing at random mechanism, that is the observations of missing depend on just observed values, not on unobserved values.

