15.6.3. Efficacy

Hgb Values
Central laboratory and HemoCue Hgb Values

 For reporting purposes, central laboratory Hgb values will be used, unless otherwise specified. However, if a central laboratory Hgb value is missing, a corresponding non-missing HemoCue Hgb value, which is associated with the identical subject number and visit, will be used.
Evaluable Hgb Values

 It will be used for reporting sensitivity analysis results and Hgb listings. Evaluable Hgb values will be based on on-therapy central laboratory and/or HemoCue Hgb values that are not taken within the 8 weeks following a red blood cell transfusion, a whole blood transfusion, or a non-randomized ESA medication which occurs on or after the randomization date (except protocol-specified ESA treatment in screening period). 
If an Hgb record meets at least one following criteria, the Hgb record will be regarded as non-evaluable.
 
 Blood Product Administration Date < Date of Hgb data ≤ Blood Product Administration Date + 56 (days) ESA Start Date < Date of Hgb data ≤ ESA Stop Date + 56 (days)

Hgb Values

Flowchart for Hgb analyses

- This flowchart will be applicable, unless otherwise specified
 - Basically, scheduled visits between Day 1 and Week 52 will be applicable to this flowchart, but analyses including by-visit summaries may include other scheduled visits (ie. screening and follow-up visit).
- [1] Regarding partially evaluated Hgb values, the following summaries of Hgb will include unscheduled visits:
- Summary of Time (weeks and %) within Hgb target range during the primary efficacy evaluation period
 - Summary of Number (%) of subjects who have an Hgb level of less than 7.5 g/dL
 - Summary of Number (%) of subjects who have an Hgb level of more than 13.0 g/dL and number of episodes
 - Time (in days) to reach the lower Hgb target (11.0 g/dL)

Hgb increase of more than 2.0 g/dL over any 4 weeks

- For this reporting purpose, Hgb values from central laboratory will be used as previously described.
- A subject who has at least one record with Hgb increase of more than 2.0 g/dL over any 4 weeks will be counted and all episodes will be listed.
- Hgb increase will be calculated for scheduled visits between Day 1 and Week 52 if available (i.e. Week 4 Hgb - Day 1 Hgb, Week 8 Hgb - Week 4 Hgb, ...)

Illustration of calculation (example in case of Week 12 missing, until Week 24 visit)

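### The ever/never proportions for Hgb >13.0, <7.5 and rise >2.0 g/dL ignore unequal on-therapy follow-up, and the rise >2.0 odds ratio inherits this

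*SAP*

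**What the plan says.** All three endpoints are other secondary endpoints (SAP 2.2), analysed in the ITT population (7.3.3). Section 7.3.1 lists the first of them as "Number (%) of subjects who have an Hgb level of more than 13.0 g/dL and number of episodes".

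- Above 13.0 g/dL (7.3.2): "The number and percentage of subjects who have an Hgb level of more than 13.0 g/dL during the treatment period and number of episodes" are summarized by arm.
- Below 7.5 g/dL (7.3.2), also by arm: "The number and percentage of subjects who have an Hgb level of less than 7.5 g/dL during the treatment period will be summarized by treatment".
- Values used for both (7.3.2): "On-therapy Hgb values observed in both scheduled and unscheduled visits will be included in the summary".
- Rise above 2.0 g/dL (15.6.3): "A subject who has at least one record with Hgb increase of more than 2.0 g/dL over any 4 weeks will be counted". It is calculated between adjacent scheduled visits, and an interval with a missing visit is not calculated. A treatment contrast is added (7.3.2): "For the ITT population, the odds ratio (daprodustat/epoetin beta pegol) will also be provided with its 95% CI". Section 15.6.3 takes the model from Section 7.2.5, a logistic regression on treatment, baseline Hgb and prior ESA use.

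On withdrawal, 7.3.4 says: "Any intercurrent events are taken to be irrelevant for secondary endpoints and the secondary endpoints will be summarized based on available and observed data". ITT entry needs only a baseline Hgb and one scheduled post-baseline Hgb (Section 4). The on-therapy window for Hgb closes one day after the treatment stop date (15.4.1.1).

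These excursion endpoints have no censoring rule, exposure-adjusted rate or time-to-event display. Time to reach 11.0 g/dL, in the same sections, is analysed by Kaplan-Meier with censoring.

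**The concern.** An ever/never proportion over a planned 52 weeks estimates 52-week risk only if everyone is observed for 52 weeks. Here a subject who stops at Week 8 without an event contributes the same zero as a completer without an event. Both observed proportions are then too low, and the arm with more early stopping is lowered more.

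The endpoints are meant to describe Hgb control with epoetin beta pegol as comparator, so readers will compare the arms. For rise >2.0 the SAP itself makes the comparison, with an odds ratio and 95% CI. The borrowed model counts a missing outcome as non-response. That penalizes dropout when the outcome is desirable. Here the event is undesirable, so an unobserved event helps the arm that lost the subject.

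**Working it through.** **Inputs.** The SAP gives no event rate or withdrawal rate for these endpoints, so there is no planned figure to reproduce. Assumed: true 52-week risk R of 10%, 30% or 50%, the same in both arms, and 52-week withdrawal d of 10% vs 20%, 10% vs 30% or 20% vs 40%. Event and withdrawal hazards are taken as constant and independent.

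**Formula.** On a 52-week time unit, l = -ln(1-R) and m = -ln(1-d). The observed ever/never proportion is

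p = l/(l+m) × [1 - exp(-(l+m))].

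**Example, R = 30%** (l = 0.3567):

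- d = 10%: m = 0.1054; p = 0.3567/0.4620 × (1 - 0.70×0.90) = 0.772 × 0.37 = 28.6%.
- d = 20%: m = 0.2231; p = 0.3567/0.5798 × (1 - 0.70×0.80) = 0.615 × 0.44 = 27.1%.
- Odds ratio, higher over lower withdrawal: (0.271/0.729)/(0.286/0.714) = 0.93. The correct value is 1.00.

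**All cases, odds ratio (higher/lower withdrawal):**

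| True risk, both arms | 10% vs 20% | 10% vs 30% | 20% vs 40% |
|---|---|---|---|
| 10% | 0.94 | 0.88 | 0.87 |
| 30% | 0.93 | 0.86 | 0.84 |
| 50% | 0.91 | 0.82 | 0.81 |

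With equal withdrawal the odds ratio is 1.00 and only the level falls (30% becomes 28.6% at 10% withdrawal in both arms).

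**Check under another withdrawal pattern.** With withdrawal times uniform over the year for a fraction w, p = (1-w)R + w[1 - R/l]. For R = 30%, the bracket is 1 - 0.30/0.3567 = 0.159. At w = 10%, p = 0.270 + 0.016 = 28.6%; at w = 25%, p = 0.225 + 0.040 = 26.5%. The odds ratio is 0.90, in line with the table.

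**Missing visits.** In the SAP's own illustration for rise >2.0 (15.6.3, Week 12 missing), the changes are 0.7, 2.1, not calculated, 0.1 and -0.4. Day 1 to Week 24 has six 4-week intervals, of which four are evaluable, and one qualifies. A subject whose last value is at Week 8 has two of the 13 intervals to Week 52. Neither number enters the odds ratio.

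**Window by arm.** For withdrawals, the daprodustat stop date is the recorded one, while the comparator's is assumed to be the last dosing date plus 13 or 27 days (15.6.1). On-therapy follow-up after early stopping is thus not measured the same way in both arms.

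**Episodes above 13.0 g/dL.** Section 7.3.2 says which values enter but not what opens or closes an episode. The series 12.1, 13.4, 13.6, 13.2, 12.6 gives 3 if each high value is an episode and 1 if each continuous excursion is.

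**The case against.** The number (%) of subjects ever having an event is the endpoint as defined, not a slip. These are complementary or exploratory comparisons without multiplicity control (5.5), and only rise >2.0 has a treatment contrast. The plan also gives context: proportions within, above and below target at each visit, time above range in Weeks 40-52, and listings of every subject with an excursion. The bias needs unequal withdrawal, which is assumed. At a rough 143 per arm (half of the approximately 286 ND subjects planned), the 95% CI around an odds ratio of 0.90 would run from about 0.54 to 1.51, so the shift is small beside sampling error. All of this stands and limits the weight of the point. None of it supplies a follow-up-adjusted figure.

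Leaving an interval with a missing visit uncalculated is also right in itself: in the SAP's illustration the gap runs from Day 61 to Day 127, which is not a 4-week change. The issue is only that lost intervals are not counted anywhere.

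A reader might go further and infer that the SAP counts every value above 13.0 g/dL as an episode, so that one long excursion, or a recheck of it, adds several. The text does not support this. Section 7.3.2 states only which values are used. The phrase in 15.6.3, "will be counted and all episodes will be listed", belongs to the rise >2.0 endpoint, where episodes are listed and not tallied. Values below 7.5 and rises above 2.0 are subject proportions, which repeated records cannot inflate. The definition may also sit in the mock shells, which are separate documents, or in the protocol, which is not at hand.

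**Conclusion.** The point holds for the three subject proportions, and most directly for the rise >2.0 odds ratio. That early leavers count as event-free follows from the population, window and observed-data rules together; the SAP does not state it as an instruction. Under equal true risk, unequal withdrawal alone moves the odds ratio to about 0.81-0.94, on assumed risks of 10-50%, the assumed withdrawal pairs and constant hazards; with equal withdrawal there is no shift. Nothing in the SAP indicates which arm would benefit, so no bias toward daprodustat should be inferred. The primary and principal secondary analyses are unaffected. The missing definition of an episode above 13.0 g/dL is a secondary clarification. Weight: a cheap improvement.

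**What to change.** In SAP 7.3.2 and 15.6.3, keep the n (%) and the odds ratio and add beside them:

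1. Kaplan-Meier cumulative incidence to Week 52 by arm for >13.0, <7.5 and rise >2.0, with event-free subjects censored at their last on-therapy Hgb. The method is already planned for time to 11.0 g/dL, where censoring is at the treatment stop date. The last Hgb is preferable here because the comparator's stop date after withdrawal is assumed and can run past the last measurement.
2. For rise >2.0, qualifying intervals per evaluable 4-week interval by arm, an evaluable interval being two adjacent scheduled visits with usable Hgb. This serves as a check on the odds ratio.
3. A definition of an episode above 13.0 g/dL: a run of consecutive on-therapy values above 13.0 closed by the first value at or below 13.0, so that an unscheduled recheck extends an episode and does not add one. State how a missing visit inside a run is handled, and report episodes per patient-year of on-therapy follow-up.

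Cost: SAP wording and a few extra columns in Tables 2.46-2.57, with no new data. The Kaplan-Meier figures carry the usual assumption of non-informative censoring, which should be stated with the tables.

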7.3.2. Summary Measure

Hgb at each assessment visit

The values will be summarized using mean, standard deviation, 95%CI, minimum, P25, median, P75, and maximum at each assessment visit by treatment group. The summary will also be provided by prior ESA use, prior ESA dose, prior ESA type, and ERI. Graphical summaries will be provided using mean and 95% CI over time. The graphical summaries will also be provided by prior ESA use. The value at Wk2 (only for Cohort 3) will be provided only in summary (not in graphical summary).

Change from baseline at each assessment visit

The values will be summarized using mean, standard deviation, 95%CI, minimum, P25, median, P75, and maximum at each assessment visit by treatment group. The summary will also be provided by prior ESA use, prior ESA dose, prior ESA type, and ERI. Graphical summaries will be provided using mean and 95% CI over time. The graphical summaries will also be provided by prior ESA use. The value at Wk2 (only for Cohort 3) will be provided only in summary (not in graphical summary).

Number (%) of subjects by Hgb change from baseline category at Week 2 and 4

The number and percentage of subjects within each category will be provided by treatment group and the categories will be classified into 6 (i.e., ≤ -1 , > -1 to -0.5 , > -0.5 to 0 , > 0 to 0.5 , > 0.5 to 1 , > 1 g/dL for Week 2, ≤ -2 , > -2 to -1 , > -1 to 0 , > 0 to 1 , > 1 to 2 , > 2 g/dL for Week 4). In addition, 'within ± 1 g/dL (i.e., ≤ -1 and ≥ 1)' and 'over ± 2 g/dL (i.e., < -2 and > 2)' categories for Week 4 and 'within ± 0.5 g/dL (i.e., ≤ -0.5 and ≥ 0.5)' and 'over ± 1 g/dL (i.e., < -1 and > 1)' categories for Week 2 will be provided. The summary will also be provided by prior ESA use, prior ESA dose, prior ESA type, and ERI.

Number (%) of subjects with Hgb within the target range at each assessment visit

The number and percentage of subjects with Hgb within, above and below the target range will be summarized at each assessment visit by treatment group. Graphical summaries over time will also be produced.

Time (%) in Hgb target range during the primary efficacy evaluation period

The time (weeks and percent) within/above/below the target range will be summarized by treatment group using mean, standard deviation, minimum, P25, median, P75, and maximum. For the ITT population, the treatment differences (daprodustat – epoetin beta pegol) and the associated 95% CIs for the time (weeks and percentage) within the target range will also be provided. See Section 15.6.3 for details. The summary will also be provided by prior ESA use.

Time (in days) to reach the lower Hgb target (11.0 g/dL)

The time (days) to reach the lower Hgb target will be summarized by treatment group using P25, median, and P75 by Kaplan-Meier method. Kaplan-Meier plot of time to event will be provided using on-therapy Hgb values including unscheduled visits. Subjects who could not reach lower target will be regarded as censored. Subjects who have baseline central laboratory Hgb ≥ 11.0 g/dL will be excluded in this analysis. The summary will also be provided by prior ESA use.

Number (%) of subjects who have an Hgb level of less than 7.5 g/dL

The number and percentage of subjects who have an Hgb level of less than 7.5 g/dL during the treatment period will be summarized by treatment group. On-therapy Hgb values observed in both scheduled and unscheduled visits will be included in the summary.

Number (%) of subjects who have an Hgb increase of more than 2.0 g/dL over any 4 weeks

The number and percentage of subjects who have an Hgb increase of more than 2.0 g/dL over any 4 weeks (excluding Week 2) during the treatment period will be summarized by treatment group. For the ITT population, the odds ratio (daprodustat/epoetin beta pegol) will also be provided with its 95% CI. On-therapy Hgb values will be used for the summary. See Section 15.6.3 for details.

Number (%) of subjects who have an Hgb level of more than 13.0 g/dL and number of episodes

The number and percentage of subjects who have an Hgb level of more than 13.0 g/dL during the treatment period and number of episodes will be summarized by treatment group. On-therapy Hgb values observed in both scheduled and unscheduled visits will be included in the summary.

Scatter plot of Hgb assessments: Central Laboratory vs. HemoCue

A scatter plot of Hgb values measured by Central Laboratory versus Hgb values measured by Hemocue will be produced along with Pearson's correlation coefficient. Regardless of visit and treatment group, all available pairs of Hgb (i.e. non-missing values in both from central laboratory and from the corresponding HemoCue measurement) will be used.

- **Dose adjustment**

The dose adjustment algorithm is described in Section 15.6.3, based on HemoCue Hgb values.

Dose at each assessment visit / final visit

Dose at each assessment visit and final visit will be summarized by treatment group using mean, standard deviation, minimum, P25, median, P75, mode, and maximum at each assessment visit. The final visit will be the last visit of treatment exposure for each subject. Mean dose during Week 40 to 52 will also be summarized and includes subjects who has at least one exposure record during Week 40 to 52. The summary will also be provided by Prior ESA use, prior ESA dose, prior ESA type, and ERI.

Duration (days) of treatment interruption due to Hgb >13.0 g/dL

The number and percentage of subjects who have a period of treatment interruption due to Hgb >13.0 g/dL will be summarized by treatment group. On subjects who have a period of treatment interruption due to Hgb >13.0 g/dL, the duration (in days) of treatment interruption due to Hgb >13.0 g/dL per subject will be summarized by treatment group using mean, standard deviation, minimum, P25, median, P75, and maximum. On-therapy Hgb values observed in scheduled visits will be counted in the summary. The summary will also be provided by prior ESA use.

Dose adjustment

The number and percentage of subjects with dose adjustments will be provided. Number of dose adjustments will be summarized by treatment group using mean, standard deviation, minimum, median, mode, and maximum. For dose adjustments frequency, the number and percentage of subjects will be provided by the number of dose adjustments (i.e. zero, one, two, three, four, ..., ten, eleven, and twelve or more; may be refined) by treatment group during the whole treatment period. For timing of dose adjustments, the

number and percentage of subjects with dose adjustments by each assessment visit will be provided by treatment group. The summary will also be provided by Prior ESA use.

Dose adjustment to reach the lower Hgb target (11.0 g/dL)

The number and percentage of subjects with dose adjustments to reach the lower Hgb target will be provided by treatment group on the basis of on-therapy Hgb. Number of dose adjustment to reach the lower Hgb target will be summarized by treatment group using mean, standard deviation, minimum, median, mode, and maximum. For dose adjustments frequency, the number and percentage of subjects will be provided by the number of dose adjustments (i.e. zero, one, two, three, four, ..., ten, eleven, and twelve or more) by treatment group. For timing of dose adjustments, the number and percentage of subjects with dose adjustments by each assessment visit will be provided by treatment group. Subjects who do not reach the lower Hgb target during treatment period will be excluded from the summary. The summary will also be provided by Prior ESA use.

Number (%) of subjects with each dose at each assessment visit

The number and percentage of subjects with each dose will be provided. Graphical summaries of histogram will be provided with the number of subjects in each dose. Summary and histogram will be produced for each treatment group separately. For daprodustat, dose categories will be classified into 10; N/A (not available), 0 mg (treatment interruption), 1 mg, 2 mg, 4 mg, 6 mg, 8 mg, 12 mg, 18 mg, and 24 mg. For epoetin beta pegol, dose categories will be classified into 9, N/A (not available), 0 µg (treatment interruption), 25 µg, 50 µg, 75 µg, 100 µg, 150 µg, 200 µg, 250 µg. The final visit will be the last visit of treatment exposure for each subject. The summary and histogram will also be provided by Prior ESA use, prior ESA dose, prior ESA type, and ERI.

- **Hgb and Dose**

Profiles over time of Hgb and dose will be plotted for each subject.

- **Iron Use**

Dose of oral iron (mg) during the treatment period and the primary efficacy evaluation period

Monthly Average oral iron dose by quarter (See Section 15.6.3) will be summarized using mean, standard deviation, minimum, P25, median, P75, and maximum. Quarter 1 (Day 1 to Week 12), Quarter 2 (Week 12 to Week 24), Quarter 3 (Week 24 to Week 40), Quarter 4 (Week 40 to Week 52), during the screening period as baseline, and whole treatment period will be used and Quarter 4 represents the primary efficacy evaluation period. This will be also summarized by baseline iron use defined in Section 5.4.2.

Change from baseline in dose of oral iron (mg) during the treatment period and the primary efficacy evaluation period

Change from baseline in average oral iron dose (See Section 15.6.3) will be summarized using mean, standard deviation, minimum, P25, median, P75, and maximum. Quarter 1 (Day 1 to Week 12), Quarter 2 (Week 12 to Week 24), Quarter 3 (Week 24 to Week 40), Quarter 4 (Week 40 to Week 52), and whole treatment period will be used and Quarter 4 represents the primary efficacy evaluation period. For the ITT population, the treatment differences (daprodustat – epoetin beta pegol) and the associated 95% CIs will also be provided.

Number (%) of subjects who use iron during the treatment period and the primary efficacy evaluation period

The number and percentage of subjects who use iron during the screening period as baseline, the treatment period, and the primary efficacy evaluation period will be summarized separately. These will be also summarized by baseline iron use defined in Section 5.4.2

- **Iron Parameter (ferritin, TSAT, hepcidin, serum iron, and TIBC)**

Based on literature review the distributions of TSAT and hepcidin are skewed and require a log-transformation (See Section 5.2).

Raw observed value at each assessment visits

Ferritin, serum iron, and TIBC values will be summarized by treatment group using mean, standard deviation, 95% CI, minimum, P25, median, P75, and maximum at each assessment visit. TSAT and hepcidin values will be summarized by treatment group using geometric mean, standard error, coefficient of variation, and 95% CI based on log-transformed parameters, median, minimum, and maximum based on original scale at each assessment visit. Graphical summaries will also be provided for each iron parameter. These will be also summarized by baseline iron use, prior ESA use.

Change from baseline at each assessment visit

Change from baseline in ferritin, serum iron, and TIBC values will be summarized by treatment group using mean, standard deviation, 95% CI, minimum, P25, median, P75, and maximum at each assessment visit. Percent Change from baseline in TSAT and hepcidin values (Section 5.2) will be summarized by treatment group using geometric mean, coefficient of variation, and 95% CI based on log-transformed parameters, minimum, median, and maximum based on original scale at each assessment visit.

Treatment differences (daprodustat – epoetin beta pegol) and the associated 95% CIs for change from baseline will be provided at each assessment (See Section 7.3.5). For ferritin, serum iron, and TIBC change from baseline, graphical summaries will be provided by treatment group using the adjusted means and the associated 95% CIs over time. For TSAT and hepcidin percent change from baseline, graphical summaries will be provided using the adjusted geometric means percent change from baseline and the associated 95%

CIs over time. For the ITT population, Except for the graphical summaries, these will be also summarized by baseline iron use, prior ESA use, and both them. The graphical summaries will also be provided by only baseline iron use.

